At the time of surgery, anesthesiologists document the timing of key clinic information (induction, intubation, start and end of surgery, emergence, extubation, and exit of the operating room), medications and fluids administered, estimated blood loss, and type of anesthesia into the intraoperative record. Hemodynamic factors are automatically recorded into the database every minute. The following intraoperative hemodynamic factors will be included in model building:

Table 1. Exposures

Blood pressure	
Since there is no universal definition of low blood pressure under anesthesia, we will use several different variables to determine the most significant exposure by threshold and duration. Both Systolic Blood Pressure (SBP) and Mean arterial pressure (MAP) have been used in blood pressure research (12). In a recent study (26), different blood pressure modeling techniques on the same dataset led to different conclusions on the impact of hypotension on postoperative myocardial infarction and kidney injury. Methods with the largest odds ratios were absolute maximum decrease in MAP and mean episode area under threshold. However, since the area under threshold is less interpretable and difficult to calculate in everyday clinical practice, the duration under threshold will be used.
 
SBP
 
1. Maximum change from preoperative SBP, in a) absolute change (mmHg), and b) relative change (%) (emergency and elective cases analyzed separately due to the lack of preoperative blood pressure in the emergency group)2. Cumulative duration (minutes) $\geq 20\%$ below preoperative SBP3. Longest single episode (minutes) below a) 80, b) 90, and c) 100 mmHg4. Cumulative duration (minutes) below a) 80, b) 90, and c) 100 mmHg 
MAP
 
1. Maximum change from preoperative MAP, in a) absolute change (mmHg), and b) relative change (%) (emergency and elective cases analyzed separately due to the lack of preoperative blood pressure in the emergency group. Note that since the HSM database only contains SBP and DBP, not MAP, MAP will be calculated using $MAP = 1/3*SBP + 2/3*DBP$)2. Cumulative duration (minutes) $\geq 20\%$ below preoperative MAP3. Longest single episode (minutes) below a) 60, b) 65, c) 70, and d) 80mmHg4. Cumulative duration (minutes) below a) 60, b) 65, c) 70, and d) 80mmHg
-----------------------	---

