 5. Delirium
 6. Septic Shock
2. Postoperative ICU admission (yes/no)
3. Prolonged Postoperative Length of Stay (LOS) (greater than vs. less than or equal to CIHI Expected Length of Stay (ELOS) as assigned by the Case Mix Grouping) [note that the LOS includes the day of surgery]
4. Hospital readmission within 30 days (yes/no)
5. Intraoperative mortality (yes/no)
6. Days alive and out of hospital at 30 days postoperatively (28)

III. Other predictors included into model

The following potential perioperative predictors will be evaluated as covariates during model building. Statistically significant predictors will be retained in the model.

Table 2. Other predictors

Preoperative	
 1. Demographics: age on date of surgery, sex, obesity (body mass index>30) 2. Indicators of preoperative comorbidities: since no comorbidity score has perfect performance, a variety of models will be evaluated and the most significant predictive score will be retained in the model. 
 • American Society of Anesthesiologist class • RCRI score(29), and specific components via ICD codes (history of ischemic heart disease, congestive heart failure, cerebrovascular disease, diabetes, chronic kidney disease, and CCI and Case Mix Group codes of suprainguinal vascular, intraperitoneal, or intrathoracic surgery) using previously published methods (30)(31) • Elixhauser comorbidity index (32) and Charlson Comorbidity Index (33): calculated using diagnoses from the previous three years according to standard algorithm by HDNS. Reported as both total score and individual categories • Hospital Frailty Risk Score (34): based on ICD codes • Preoperative blood pressure: ICD diagnosis of hypertension and by measured blood pressure • Preoperative heart rate: Innovian and HSM • Chronic Obstructive Lung Disease (ICD code): since it may affect the interpretation of results of SpO₂ and EtCO₂ 3. Indicators of surgical complexity 
 • CIHI DAD Case Mix Group (CMG) class (also contains categories that include medical complexity) • Main Surgical Service • Procedural Index for Mortality Risk (PIMR) (35): according to CCI • Procedure: CCI codes • Preoperative ICU admission • Emergency surgery: as determined by DAD Method of Entry = emergency department or transferred from another institution)

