Since intraoperative hemodynamics are automatically recorded and mortality reporting is mandatory, we do not expect significant missing data for the key hemodynamic predictors and primary outcomes. For disease conditions, patients without ICD codes are assumed to not have the disease; the same applies for medications. For the other variables of interest, if there is less than 5% missing data, no processing will be performed. Between 5-20%, missing data will be imputed using group mean (43) for continuous variables. At greater than 20% missing data, the variable will be removed from analysis with potential causes evaluated and reported.

Creating the models

We will divide the cohort temporally (approximately 80:20 ratio) into two groups: derivation/training group (approx. January 1, 2013 – Dec 31, 2016), and validation group (approx. Jan 1, 2017 – December 1, 2017). This temporal approach to the model building vs. validation groups will also mirror the real-life application of machine learning, where data from the past is used to predict future outcomes. Splines will be used for the hemodynamic predictors involving time as a unit.

In the derivation/training set, we will create models for the *primary outcome* using machine learning techniques, including logistic regression with variable selection, classification trees, and Principal Component Analysis (PCA)(21). We have chosen these techniques to obtain interpretable results, i.e. being able to understand the process by which the algorithm decision making occurred. Also, these techniques demonstrate different approaches and perspectives to better understand the relationships amongst the variables.

Logistic regression with variable selection (e.g. LASSO, Elastic Net) identifies the most important predictors to create a parsimonious model. Classification trees predict outcomes based on input variables through classification. Random forest is an ensemble method of classification trees; while it is not directly interpretable, it can show which predictor has the highest importance. Association rule learning will be used to find new patterns. PCA is used for

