The performance of all models created will be evaluated in the validation set as part of internal validation using the same metrics of discrimination, calibration, and risk reclassification, and compared to the Surgical Apgar Score. Since there will likely be significant class imbalance and ROC curves may overestimate model performance, for each model, precision and recall curves (PRC), F score, average precision, and AUC will also be reported and compared. The best performing model will also be used to analyze for predictors for secondary outcomes. Sensitivity (recall, true positive rate), specificity, positive predictive value (precision), G-mean, negative predictive values, False Discovery Rates (FDR), optimism, and measures of association of hemodynamic thresholds for primary and secondary outcomes will be computed. Bayesian network causal inference analysis may be performed, to help increase interpretability.

Sensitivity and subgroup analysis

Sensitivity analysis will be performed for different definitions of hemodynamic derangements. Subgroup analysis will be performed based on age, sex, high preoperative risk (most significant indicator of preoperative comorbidity in Table 2, based on final model), RCRI, frailty (HFRS), preoperative hypertension, a select list of intermediate-high risk, gender-neutral elective surgery (please see Appendix – RCRI Protocol Table 1), emergency surgery, and type of anesthesia.

Power calculation

The 2016-2017 in-hospital mortality after major surgery in Nova Scotia is 1.7% (47). Using the Events Per Variable criterion (EPV) of at least 10 outcomes per predictor in the sample, the 1.7% mortality (408) out of an estimated sample size of 24,000 for the derivation/training group means that our model would be valid for up to 41 predictors for the primary outcome. However, the EPV may over or underestimate the limitations of the EPV criterion (48), square root of the mean squared prediction error (rMPSE) and mean absolute prediction error (MAPE) will be calculated based on the number of predictors, sample size and events fraction (49) with the caveat that this model has not been externally validated. Full power calculation will be performed once we receive the final sample size.

Strengths

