Innovian	Preoperative heart rate	Patient	Jan 1, 2013 to Dec 1, 2017	
As this may affect the level of harm from the intraoperative heart rate, it will be used in the calculation of change in heart rate (absolute and %)
 
HSM contains heart rate of elective surgery patients at the anesthetic clinic and prior to entering the operating room, while Innovian contains the initial heart rate of all patients in the operative room. The lowest heart rate from either Innovian or HSM will be used.

CIHI DAD	
Emergency surgery
 
[Derived by HDNS]
 
ENTRYCO D: method of entry
	Patient	Jan 1, 2013 to Dec 1, 2017	ENTRYCOD = E (i.e. emergency department) and/or ADFROM = [any except 085 (QEII) – i.e. transferred from another institution] excluding elective admission (flag) will be used to identify surgeries as emergency surgery. As the emergency nature of surgery has been shown to affect outcomes, it will be included as a covariate.

	ADFROM: Institution from Number			
CIHI DAD	ADTYPE: Admission Type	Patient	Jan 1, 2013 to Dec 1, 2017	This variable will be used internally by HDNS to create a flag for elective admission. This will not be included in the dataset. This will help identify patients who did not have emergency surgery.
Indicator of surgical complexity				
CIHI DAD	CMG: Case Mix Group (“a grouping methodology developed by CIHI that categorizes acute care patients into groups based on similarities of diagnosis, intervention, LOS, and resource requirements.”)	Patient	Jan 1, 2013 to Dec 1, 2017	All CMG will be included into modeling to determine the CMG with the highest postoperative risk.
CIHI DAD	PIMR: Procedural Index for Mortality Risk [Derived by HDNS]	Patient	Jan 1, 2013 to Dec 1, 2017	As the PIMR has been shown to affect outcomes, it will be included as a covariate. HDNS will calculate using DXCODE according to a published protocol (35). Detailed protocol will be sent to the HDNS.
CIHI DAD	Subgroup analysis flag: intermediate to high risk, gender neutral elective surgeries	Patient	Jan 1, 2013 to Dec 1, 2017	To create a list of intermediate to high risk, gender neutral elective surgeries for subgroup analysis. Detailed list of CCI codes will be sent to the HDNS.

	[Derived by HDNS based on PCODE]			

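### The 41-predictor ceiling is never set against the candidate list, which holds about 69 to 140 terms before splines and procedure codes, so events per variable is about 6 down to 3 rather than 10

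*Combined protocol and SAP*

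**What the plan says.** The Power calculation section works from a criterion: "Using the Events Per Variable criterion (EPV) of at least 10 outcomes per predictor in the sample". It takes "the 1.7% mortality (408) out of an estimated sample size of 24,000 for the derivation/training group" and concludes that this "means that our model would be valid for up to 41 predictors for the primary outcome". It then acknowledges that EPV can mislead in either direction, promises rMPSE and MAPE based on the number of predictors, and defers a full power calculation until the final sample size is known. It gives no count of the predictors to be tried.

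The list of predictors is elsewhere:

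- **Variables, I. Main Predictors, Table 1**: "The following intraoperative hemodynamic factors will be included in model building". Several blood pressure definitions are listed so that the most significant threshold and duration can be found.
- **Variables, III. Other predictors, Table 2**: covariates are evaluated and kept if statistically significant, and the most significant comorbidity score is kept. For the Elixhauser and Charlson indices the table says "Reported as both total score and individual categories".
- **Creating the models**: "Splines will be used for the hemodynamic predictors involving time as a unit". The number of knots is not given. LASSO and Elastic Net are named as examples of variable selection.
- **Appendix 1**: "All CMG will be included into modeling to determine the CMG with the highest postoperative risk". The procedure code is also a covariate.

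**The concern.** A reader of the Power calculation section would conclude that the derivation set supports the planned modelling. That holds only if about 41 or fewer parameters are tried, and the plan's tables list many more.

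The number of terms left in the final model does not settle the matter. When exposures, scores and covariates are chosen by their significance for the outcome, every candidate screened contributes to overfitting, including those later dropped. With few deaths per candidate, the selected set is unstable and the associations that survive tend to be exaggerated. A main aim is to say which vital signs, at which levels, may be harmful, so exaggerated or unstable threshold associations would affect the central output as well as the prediction score.

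**Working it through.** **1. The plan's own figure.** Expected deaths = 24,000 × 0.017 = 408. Ceiling at EPV 10 = 408 / 10 = 40.8, rounded to 41. This reproduces.

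**2. Exposure terms (Table 1).**

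| Group | Count | Terms |
|---|---|---|
| SBP | 2 + 1 + 3 + 3 | 9 |
| MAP | 2 + 1 + 4 + 4 | 11 |
| Heart rate | 2 + 2 + 1 + 2 + 2 | 9 |
| Medications | 5 | 5 |
| SpO₂ | 2 + 2 | 4 |
| EtCO₂ | 2 + 2 | 4 |
| **Total** | | **42** |

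If positive and negative heart-rate change count as one term for each of the two items, heart rate gives 7 and the total is 40. Of the 42, 28 are durations in minutes (SBP 7, MAP 9, heart rate 4, SpO₂ 4, EtCO₂ 4).

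**3. Covariate terms (Table 2 and Appendix 1), without Case Mix Groups, procedure codes or splines.**

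- *Full count, 98*: demographics 3; ASA 4 dummies; RCRI total and 6 components, 7; Elixhauser total and 31 categories, 32; Charlson total and 17 categories, 18; frailty score 1; hypertension 1; preoperative SBP and MAP 2; preoperative heart rate 1; COPD 1; surgical service 11 (12 listed levels); PIMR 1; preoperative ICU 1; emergency 1; anesthesia type 4; MAC 1; BIS 1; temperature 2; crystalloid 1; duration 1; laparoscopy 1; bleeding 3.
- *Index totals only, ASA as one term, 41*: 98 − 3 (ASA) − 6 (RCRI) − 31 (Elixhauser) − 17 (Charlson).
- *Generous count, 27*: 41 − 4 (one comorbidity score instead of five) − 10 (service as one term).

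**4. EPV = deaths / candidate terms.**

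| Count | Terms | EPV with 408 deaths |
|---|---|---|
| Generous | 42 + 27 = 69 | 5.9 |
| Index totals only | 42 + 41 = 83 | 4.9 |
| Full | 42 + 98 = 140 | 2.9 |

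**5. Splines.** The plan gives no knots, so assume 3 df per duration, which adds 2 × 28 = 56 terms. Full count: 140 + 56 = 196, EPV = 408 / 196 = 2.1. Generous count: 69 + 56 = 125, EPV = 408 / 125 = 3.3. Case Mix Groups and procedure codes would lower both, but the documents do not give the number of levels.

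**6. A larger derivation set.** The plan describes about 35,000 patients split roughly 80:20, and 0.8 × 35,000 = 28,000 rather than 24,000. Then deaths = 28,000 × 0.017 = 476 and the ceiling is 47.6. EPV = 476 / 140 = 3.4 (full) or 476 / 69 = 6.9 (generous). With Table 1 also counted as 40, it is 476 / 67 = 7.1.

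**7. What would meet the rule.** One definition per exposure in the Hypothesis section (MAP <65; heart rate <60 and >100; medications; SpO₂ <88; EtCO₂ <30 and >45: 7 terms) plus the 27 generous covariates gives 34 terms, and 408 / 34 = 12.0. The plan does not specify that model.

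**The case against.** Several points on the other side stand.

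- *The arithmetic is right.* A reader might infer a calculation error. There is none, and the plan does not say that its full list achieves EPV 10. The gap is a comparison not made.
- *Table 1 on its own.* One might say that the exposures alone break the rule, since 408 / 42 = 9.7. That depends on splitting the heart-rate changes by direction. Counted as 40 terms, 408 / 40 = 10.2. With 476 deaths, 476 / 42 = 11.3.
- *A firm EPV of 2 to 3.* This needs the index categories counted in full, particular codings for ASA, service and anesthesia type, and an assumed spline. Many terms are alternative definitions or overlapping comorbidities. The Appendix wording on categories may be partly a data-delivery request. Variables with over 20% missing would be dropped. Only a range is supportable.
- *A need for about 82,000 patients.* Ten deaths for each of 140 terms means 1,400 deaths, or 1,400 / 0.017 ≈ 82,353 patients. The documents do not support this as a requirement, because they specify no single unpenalised 140-term model.
- *The PCA route.* The second PCA uses predictors only, so its reduction is blind to the outcome. Terms it discards do not count against EPV in the logistic regression that follows.
- *Safeguards.* LASSO and Elastic Net are penalised. Cross-validation, temporal validation, reported optimism and the promised rMPSE and MAPE would help to reveal overfitting. EPV 10 is a rule of thumb that the plan itself questions.

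These points narrow the concern without removing it. The promised error measures depend on a predictor count that the plan never states, and the deferred power calculation waits on sample size only. Validation would expose poor prediction but would not repair unstable selection or inflated associations. Tables 1 and 2 still describe selection by significance, with no penalty stated there.

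**Conclusion.** The concern holds as a gap between the stated ceiling and the candidate list. For the outcome-driven selection described with Tables 1 and 2, EPV is about 5.9 (69 terms) down to 2.9 (140 terms). With an assumed 3-df spline per duration these become about 3.3 and 2.1. No count of the described list reaches 10; the most favourable combination gives 7.1.

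This rests on the plan's 1.7% event rate, which is an in-hospital figure used for 30-day mortality, and on counting candidates rather than retained terms. The rate would have to be well above 1.7% to change the conclusion: 69 terms need 690 deaths, or 690 / 24,000 = 2.9%.

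A reader might go further and infer that every planned model is overfitted or that the study is too small. The documents do not support that, because penalised fits and outcome-blind reduction are among the planned methods. What fails is the adequacy statement as applied to significance-based selection.

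**What to change.** 1. **Power calculation**: state the number of candidate parameters, including dummy and spline terms, and the EPV range that results. Say that EPV 10 is not met for the full list, and base the promised rMPSE and MAPE on that count.
2. **Variables, III**: replace retention by statistical significance with penalised selection (the LASSO or Elastic Net already named under Creating the models) for any model that uses the full list.
3. **Evaluating model performance**: report optimism-corrected performance with the whole selection process repeated in each resample, including the choice of exposure definition and comorbidity score.
4. **Shortening the list**: make any reduction before modelling without using the outcome, for example index totals instead of totals plus every category.

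The threshold and duration comparisons and the Case Mix Group analysis are stated aims and can stay within the penalised models. Forcing one duration metric per vital sign, or dropping Case Mix Groups, would be a trade-off for the investigators and is not needed here.

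Cost: changes to the text, a little more analysis work, and a less favourable adequacy statement. No new data are required.

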This is a minimal-risk study. De-identified patient data meeting the inclusion and exclusion criteria will be obtained from Innovian and Health Data Nova Scotia. This project satisfies all of the requirements for waiver of consent under the Tri-Council Policy Statement (TCPS 2) and Nova Scotia Personal Health Information Act (please see Request for Waiver of Consent appendix). The population size is estimated to be 35,000, which would be impracticable since this is an incredibly large population to contact for consent. Also, the cohort of interest includes patients aged 45 and older who have undergone surgery, and it is therefore expected that some patients would have died. Obtaining consent for these individuals would not only result in the re-identification of these patients, but also their next-of-kin who would give consent on their behalf. We have submitted a request for waiver of consent to the REB.

Measures will be in place to minimize the risk of breach in privacy and confidentiality (please see below). Due to the large sample size and the collection of common perioperative outcomes, accidental identification of a specific person from de-identified data is unlikely. There is no other adverse event, harm, or risk anticipated.

Health Data Nova Scotia will create a database of linked data using the Provincial Health Card number and date of surgery. The database we receive will be de-identified. PHI collected include the following and will be used in the most de-identified form:

1. Date of surgery (for patients with multiple surgeries, information from only the first surgery will be collected): in order to divide the cohort into derivation, training, and validation groups by date of surgery
2. Age on date of surgery, Sex: potential covariates in the model
3. Procedures (Current Procedural Terminology (CPT) codes: a potential covariate in the model

Measures Taken to Protect Personal Health Information and Study Data

- **Cohort creation:** The linked dataset will be created by HDNS through experienced personnel and established process, and follow Tri-Council guidelines. The dataset we receive for analysis will not contain any direct identifiers such as health card number and date of birth.
- **Controlled access:** Only authorized researchers in Nova Scotia will have access to de-identified person-level data. Aggregate data will be used as early as possible. While [name] is in Boston, if needed, Health Data Nova Scotia will perform data analysis on patient-level data using SAS protocol from team and send the rest of the team aggregate data for interpretation. The rest of the team will only have access to aggregate results after statistical analysis, with no identifiable information. All de-identified person-level electronic data will be securely stored in the HDNS secure server “Citadel”, where analysis will be performed without needing to download data from the secure server.

- Details from HDNS regarding Citadel: "Analyses will be carried out remotely on the HDNS Windows server "Citadel". Connection to Citadel occurs through Remote Desktop Connection (RDC). Citadel only accepts connections from approved DAL NetIDs to access specific project data housed in our Hadoop based research cluster. Other external connections such as the internet or USB devices are disabled, and no data may be transferred between the local PC and the remote session."
- **Removal of all personal identifiers in electronic data:** This will be performed by the HDNS prior to the release of the analytic dataset to the project team.
- **The results of the study (prototypes, publications, posters, presentations) will not contain any personal data:** Only aggregate data of cell counts greater than 5 will be reported. As per HDNS policy, manuscripts will be submitted to HDNS for approval prior to publication to ensure privacy and confidentiality.

Storage and Retention of Personal Health Information and Study Data

De-identified electronic person-level data will be securely stored in Citadel, the HDNS server. (please see above). Paper material will be stored in a locked cabinet in the Halifax Infirmary Anesthesiology Research Office. Regulatory documents (no-PHI) will be stored in the secure (locked; access limited) anesthesia research office. Electronic records will be kept in password protected files on a password protected computer on the NSHealth network.

After study completion, according to HDNS protocol, researchers will no longer have access to Citadel but the data will be kept within HDNS for a minimum of seven years. Paper records will be securely shredded in accordance to NSHA policy. All electronic files will be permanently erased by the according to NSHA IT policy at the end of the retention period (7 years).

How do benefits outweigh harm

The results of this study may help synthesize complex intraoperative clinical information and unveil novel therapeutic strategies. Derived from data from the QEII Hospitals, the results would be directly applicable to the care of Nova Scotians. The QEII hospitals are tertiary referral centres taking care of some of the sickest patients of the province. Better understanding of intraoperative predictors may unveil strategies to improve outcome and improve resource allocation after surgery.

The models may lead to the creation of objective risk stratification scores calculated at the end of surgery, to identify high risk patients for increased postoperative follow-up and monitoring. Moreover, if models created using machine learning perform well, machine learning may be used more frequently to reveal the patterns within complex, large population perioperative datasets. Hemodynamics are potentially modifiable risk factors. Future research includes prospective studies on whether targeted hemodynamic goals, increased postoperative follow-up of high-risk patients, and real-time machine learning precision medicine could improve outcomes after surgeries.

With any database analysis project, a potential harm would be a breach in confidentiality and privacy. With robust measures detailed above to protect privacy and confidentiality strictly

followed, the risk of breaches is minimal. The many benefits of this study outweigh the unlikely occurrence of potential harms.

References

2. Nepogodiev et al. D. Global burden of postoperative death - The Lancet. *The Lancet*. 393(10170):401.
